---

## Abbreviations

---

AGC: Atypical glandular cells

AIS: Adenocarcinoma-in-situ

ASC-H: Atypical cells of undetermined significance, possible high-grade

ASC-US: Atypical squamous cells of undetermined significance

CI: Confidence interval

HPV: High-risk human papillomavirus

HSIL: High-grade squamous intraepithelial lesion

LBC: Liquid based cytology

LSIL: Low-grade squamous intraepithelial lesion

NCSP: National Cervical Screening Programme

PHO: Primary Health Organisation

## Trial registration and status

---

The study was prospectively registered on [ANZCTR \(ACTRN12622000699763\)](https://www.anzctr.org.au/Trial/Registration/Trial.jsp?ACTRN12622000699763) on 16/05/2022. The Universal Trial Number is U1111-1276-2570.

Recruitment for the study started on 19/8/22. At the time of writing, (January 2024) recruitment has been completed. Data analysis is in progress.

# Overview

---

## Background

In 2023, the primary cervical screening test in New Zealand changed from cervical cytology to high-risk human papillomavirus (HPV) testing. The purpose of this study is to evaluate the process involved in implementing primary HPV-based cervical cancer screening in primary care, including the option of self-testing. This will generate practical and clinically relevant information for the introduction of primary HPV testing.

## Methods

This intervention study offered people the opportunity to undergo HPV testing instead of standard cervical cytology for cervical cancer screening. Over a six-month recruitment period, people who are due or overdue for cervical screening were invited to participate. The study was conducted at general practices in New Zealand. Participants were offered the choice of a vaginal HPV self-test or a clinician-taken cervical HPV test. Data collected included the type of HPV screening test selected, the results of the HPV test, whether a referral was made for cytology and/or colposcopy, whether a cytology and/or colposcopy appointment was attended, and how long it took to complete the screening pathway.

## Discussion

This study is designed to provide an evidence-base on which practical recommendations can be developed to guide the introduction of primary HPV testing for cervical screening in New Zealand.

## Background

---

The New Zealand National Cervical Screening Program (NCSP) has successfully reduced incidence of and mortality from cervical cancer.[1] However, cervical cancer incidence has changed little in the last 20 years.[1] Additionally, the outcomes of screening are inequitable, with Māori and Pacific people experiencing higher cervical cancer incidence and mortality.[1] Up until recently, the primary screening test for cervical cancer in New Zealand was cervical cytology. However, in 2023, the NCSP introduced high risk human papillomavirus (HPV) testing as the primary screen, with HPV type and cervical cytology used to triage people to further investigation or repeat screening.

Compared with cervical cytology, HPV testing results in earlier detection of precancerous abnormalities and greater protection against cervical cancer.[2, 3] The HPV test has the option of being performed as a self-test, using a swab to take a sample from the vagina. Alternatively, it can be performed as a clinician-taken test from the cervix, using a cervical sampler and a liquid-based cytology (LBC) medium.

There is evidence that vaginal HPV self-tests are more acceptable to people than cervical cytology or a clinician-taken HPV test.[4-8] HPV self-testing has been demonstrated to improve screening acceptability and uptake in Māori and Pacific people who are overdue for screening.[4-8] As a result, self-testing has the potential to improve cervical screening coverage and to improve health equity.[9]

It is expected that the introduction of HPV screening in New Zealand will increase screening uptake, identify more people with cervical abnormalities, and reduce disparities in cervical cancer incidence and mortality. This study will evaluate the process involved in implementing primary HPV-based cervical cancer screening in primary care.

## Methods

---

[figure not shown]
### Aim

The aim of this study is to evaluate the process involved in implementing primary HPV-based cervical cancer screening in primary care.

### Trial design

This single-arm intervention study offers people the opportunity to undergo HPV testing instead of standard cervical cytology. An overview of study procedures is outlined in Figure

1. Study objectives and outcomes are outlined in Figure 2.

**Figure 1. Study recruitment and procedures**

GP: General Practitioner, HPV: High risk human papillomavirus, LBC: Liquid based cytology, NCSP: National Cervical Screening Programme, PHO: Primary Healthcare organisation.

**Figure 1 details**

\* Conducted at the study appointment or another time.

\*\* Taken under direct visualisation by an accredited cervical screener using a cervibroom™ or equivalent.

^ Timing is dependent on when the patient and their clinician take action. See safety section regarding time limits to ensure clinical safety with appropriate times for follow up of positive HPV results. Participants will be followed up for 3 months after closure of the 6 month recruitment period.

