# In some participants a cervical sample for HPV and cytology will be clinically recommended.

---

Objectives	Outcome measures

To describe the impact of HPV testing (by demographics and screening history when numbers permit) in terms of:
 
 
- Proportion of patients screened by each method
 
- Proportion of patients who complete or do not complete each step of the appropriate screening pathway (including uptake of screening, cytology triage, and colposcopy assessment) and referral back to primary care
 
- Screening outcomes in patients with prior abnormalities in relation to transition guideline recommendations
 
- Number of colposcopy referrals, their indication, and outcomes.
 
	
The number (and percentage) of participants that undertook a: vaginal test at home, vaginal test at their general practice without staff assistance, vaginal test at their general practice with staff assistance, cervical test without concurrent cytology, or cervical test with concurrent cytology.g
 
In participants who underwent HPV testing and had an unsatisfactory result, the number (and percentage) that: did have a repeat HPV test or did not have a repeat HPV test.
 
The reason cytology was performed in participants that had cytology results issued from the sample taken during a cervical HPV test. See figure legend for reasons.h
 
The reason cytology was performed in participants that had cytology performed after an HPV test and before colposcopy: positive for HPV result or other reason.*
 
The reason for no cytology report (prior to colposcopy) in participants positive for HPV and had a vaginal HPV test: cytology not considered feasible by the GP, participant declined, participant unable to be contacted, or other.*
 
The number (and percentage) of participants that had a referral for colposcopy by classification of urgency.*
 
In participants referred for colposcopy, the number (and percentage) that received 1, 2, 3 or >3 invitations for an appointment.*

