## **Participant inclusion/exclusion criteria**

People were eligible to take part in the study if they were enrolled as a patient in a participating general practice, eligible for cervical screening as part of the NCSP, and due or overdue for a cervical screening test within the study enrolment period.

Patients who were invited to take part in the study could participate within three months of the completion of the six-month recruitment period. Patients were excluded if they were unable or unwilling to provide informed consent.

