### **Figure 3 details**

*\*Note if a vaginal self-test is taken and the result is positive a cervical cytology specimen is indicated to stratify risk, however in some circumstances it will not change so is not required (i.e., HPV16/18 positive). If a cervical test has been taken this will be performed on the same specimen by the laboratory. It is advised that this test is performed within 2 weeks.*

*\*\*With the new five yearly screening interval, those coming in for their next screening test (after previous cytology screening) any time in the last five years before age 69, i.e., 65 – 69 years of age (inclusive), can exit the programme if their HPV test result is negative. This includes those with normal screening histories, with no screening history, and those with previous abnormalities who have already been returned to regular interval (three yearly) screening. See protocol for details of exceptions.*

[figure not shown]
*Those who would normally exit the NCSP under the current NCSP exit requirements i.e., have had two normal screening cytology samples between ages 62 and 69 years of age, can exit at 69 years of age without HPV testing (providing not immune deficient or requiring further follow-up because of abnormal results).*

*\*\*\*Urgency of referrals to Colposcopy are as follows;*

- *Very Urgent – Suspicion of Malignancy (10 working days)*
- *Urgent – High-grade cytology and/or HPV 16 or 18 positive (20 working days)*
- *Semi-Urgent – Other high-risk HPV and low-grade/ASCUS cytology (3 months)*
- *Colposcopy can be referred as a clinical override e.g., HPV other and patient declining cytology triage.*

Positive clinician-taken LBC cervical HPV samples had cytology performed by the laboratory. The result was sent to the requesting clinician and study staff, as well as directly to the NCSP by the laboratory. Positive HPV vaginal self-test samples cannot have cytology performed on them, so a separate clinician-taken cytology test at the participant's general practice was recommended.

Indications for colposcopy are outlined in Figure 4. Colposcopy was performed as per standard practice guidelines.

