## **Sample size**

It was estimated that the average New Zealand general practice would have 266 patients due for cervical screening over a six-month period and 25% of patients would decline participation in this study. As a result, approximately 15 general practices would be required to recruit 3,000 patients over a six-month screening period. Based on studies investigating the acceptability of vaginal HPV self-testing,[5, 12-14] it was estimated that 60-70% of participants would opt for a vaginal HPV self-test (1,800-2,100 participants). Results from a previous study[3] suggested that approximately 12% of HPV self-tests would be positive, which could result in an estimated 216-252 participants being invited to return to their general practice for cervical cytology. With a sample size of 216 participants with a positive HPV result, there was 95% power to observe a failure to return rate of 2% or more. This is one of multiple clinically meaningful outcomes measured in this study (Figure 2). As this outcome

requires the largest sample size, it was used to determine that recruitment of 3,000 participants would be required.

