## Table A1. Full list of study outcomes

Please note, as appropriate, data will be presented separately by whether the participant opted for:

- Vaginal high risk human papillomavirus (hrHPV) self-test performed at home or other suitable location
- Vaginal HPV self-test performed at the general practice with or without support/assistance from a nurse or doctor.
- Clinician-taken cervical HPV test.

Outcomes relate to all participants unless otherwise stated.

---

### Primary outcome 1

The number (and percentage) of participants that undertook a:

- Vaginal test at home
- Vaginal test at their General Practice (GP) clinic without staff assistance
- Vaginal test at their GP clinic with staff assistance
- Cervical test without concurrent cytology
- Cervical test with concurrent cytology.

Data obtained from participating GP clinics.

*Timepoint:*

By the end of screening period.

---

### Primary outcome 2

The number (and percentage) of participants who had the following high risk human papillomavirus (hrHPV) result:

- HPV 16
- HPV 18
- Other hrHPV (listed by genotype where available)
- hrHPV not detected.

Data obtained from participating GP clinics and laboratories.

*Timepoint:*

By six months after the end of the screening period.

---

### Primary outcome 3

The mean, median and range for the time between an hrHPV test report being issued and GP referral for colposcopy in all participants that had an hrHPV result that indicated requirement for referral to colposcopy.

Data to be presented separately by whether participants had a cervical or vaginal hrHPV test, and whether the referral was made with or without cytology results.

Data to also be presented separately for participants negative for hrHPV, participants positive for human papillomavirus (HPV) 16 and/or 18, and participants positive for hrHPV other than 16 or 18.

Data obtained from participating GP clinics and laboratories.

*Timepoint:*

By six months after the end of the screening period.

---

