### **Secondary outcome 37**

The number of patients at participating clinics who are due or overdue for cervical cancer screening during the six month screening period that did not take part in the study (deidentified data). Of these patients, the number (and percentage) that did have cervical cytology during the screening period and did not have cervical cytology during the screening period.

Data obtained from participating GP clinics.

*Timepoint:*

By the end of the screening period.

---

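### Follow-up ends at month 9 in Figure 1 and month 12 in Table A1, while entry stays open to month 9, so follow-up is unequal and, on Figure 1's rule, falls to zero

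*Protocol*

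**What the plan says.** All references are to the Protocol. Four statements fix the timing.

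- **End of follow-up, first statement (Figure 1 details):** "Participants will be followed up for 3 months after closure of the 6 month recruitment period".
- **End of follow-up, second statement (Table A1):** primary outcomes 2 and 3 and most secondary outcomes carry the timepoint "By six months after the end of the screening period". The Sample size section gives that period's length: "approximately 15 general practices would be required to recruit 3,000 patients over a six-month screening period". Secondary outcome 37 agrees: "due or overdue for cervical cancer screening during the six month screening period".
- **End of entry (Participant inclusion/exclusion criteria):** "Patients who were invited to take part in the study could participate within three months of the completion of the six-month recruitment period".
- **Primary outcome 1 (Table A1):** the timepoint is "By the end of screening period".

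One objective in Figure 2 is the "Proportion of patients who complete or do not complete each step of the appropriate screening pathway". The Statistical analysis section summarises discrete endpoints as counts and percentages with binomial confidence intervals and mentions censoring only for time-to-event displays. Table A1 summarises primary outcome 3, the time from HPV report to colposcopy referral, by mean, median and range. No minimum or common follow-up per participant is stated.

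**The concern.** The first statement ends follow-up on the day entry ends. Someone tested on that day has no time to return for cytology, be referred or attend colposcopy. Table A1 gives the same person three months. Nothing says which rule governs, so the same data can give different completion proportions depending on the section the analyst follows.

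Both rules are calendar cut-offs, so observation time depends on when a person entered. If the percentages take everyone who needed a step as the denominator, a person still waiting at the cut looks the same as one who never attended. Times computed among people who reached a step lose the slow cases and come out too short. Primary outcome 1 has a related fault: its timepoint is month 6, three months before entry closes, so tests taken by late entrants fall outside it.

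**Working it through.** **1. Calendar.** Count months from the start of recruitment and take entry as the date of the HPV test. Follow-up = cut-off month − entry month.

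| Rule | Cut-off | Entry at 0 | Entry at 6 | Entry at 9 |
|---|---|---|---|---|
| Figure 1 details | 6 + 3 = 9 | 9 | 3 | 0 |
| Table A1, six-month screening period | 6 + 6 = 12 | 12 | 6 | 3 |
| Table A1, if the screening period meant the nine-month entry window | 9 + 6 = 15 | 15 | 9 | 6 |

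The third row is only a possible reading; the Sample size section and secondary outcome 37 point to the second.

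**2. The Protocol's own pathway times.** Figure 3 details advise cytology within 2 weeks (14/30.44 = 0.46 months), and give 20 working days for urgent colposcopy (28/30.44 = 0.92 months) and 3 months for semi-urgent.

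- Urgent route: 0.46 + 0.92 = 1.38 months. This fits the 3-month minimum under Table A1.
- Semi-urgent route: 0.46 + 3 = 3.46 months. At a month 9 cut, anyone tested after month 9 − 3.46 = 5.54 lacks it, including every late entrant. At a month 12 cut, only those tested after month 8.54 lack it.
- Cytology alone: at a month 9 cut, those tested after 9 − 0.46 = 8.54 lack the 2 weeks. At month 12, nobody does.

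**3. Against the planning rate.** The Sample size section expects 3,000 × 0.60 × 0.12 = 216 positive self-tests (reproduced) and plans around a failure-to-return rate of 2%. Let q be the share of positives entering in months 6 to 9, spread evenly. The share without a 2-week cytology window at month 9 is q × 0.46/3.

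- q = 2%: 0.3%, or 0.7 of 216.
- q = 20%: 3.1%, or 6.6 of 216.

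The Protocol does not give q; 2% to 20% is an assumed range.

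**4. Illustration for completion through colposcopy.** Assumptions, none of them in the Protocol: 90% enter evenly over months 0 to 6 and 10% over months 6 to 9; the delay from test to colposcopy is lognormal with log-SD 0.5; 8% never attend, so true completion is 92%. Observed completion = 0.92 × the average over entry times of P(delay ≤ cut-off − entry).

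| Median delay | Cut-off | All | Late entrants | Mean among completers (true mean) |
|---|---|---|---|---|
| 4 months | 9 | 61% | 6% | 3.6 (4.5) months |
| 4 months | 12 | 82% | 53% | 4.0 (4.5) months |
| 1.8 months | 9 | 84% | 34% | 1.94 (2.04) months |
| 1.8 months | 12 | 91% | 88% | 2.02 (2.04) months |

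In the first row, people entering in months 0 to 6 are also cut short, at 67.2% observed: 0.9 × 67.2% + 0.1 × 6.4% = 61.1%. The loss is deepest in late entrants but not confined to them.

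**The case against.** The strongest reply is that Table A1 is the detailed outcome specification and the month 9 statement is only a note to a figure. On Table A1's rule everyone has at least 3 months, and with a 1.8-month median the bias almost disappears (91.4% against 92%). The 4-month median is pessimistic, since it exceeds even the semi-urgent route of about 3.5 months. All of this stands, and it limits the size. It does not settle which rule applies.

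A reader might infer more than the text supports:

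- **That late entrants have no follow-up.** Zero arises only under Figure 1's rule, and only for the very last entrants.
- **That people still waiting will be counted as failures.** No section says so. It is inferred from plain percentages combined with censoring reserved for time-to-event displays. A statistical analysis plan, not shown here, may handle pending cases. Several Table A1 outcomes are restricted to people who reached the step; these can favour fast cases but cannot turn waiters into failures.
- **That the pathway fits neither window.** Under Table A1 only the semi-urgent route exceeds the minimum, and only for people tested after month 8.54.
- **That the error falls on Māori, Pacific or hard-to-reach people.** Nothing describes who enters late. Someone invited in month 6 may simply reply in month 7.
- **That all primary outcomes are biased.** Test type and HPV result need little or no pathway follow-up. Outcome 3 ends at referral, whereas the illustration runs to colposcopy.

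**Conclusion.** The concern holds as a contradiction in timing with a predictable direction of bias. Three statements cannot all govern the same analysis, and the timepoint of primary outcome 1 precedes the close of entry. Under the month 9 rule, plain percentages for cytology, referral and colposcopy would be too low for late entrants, and times among completers too short. Under month 12 the same effects are smaller and may be negligible.

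The direction follows from the calendar, provided pending cases stay in the denominators. The size does not: in the illustration the shortfall from 92% ranges from about 31 percentage points (4-month median, month 9) to under 1 point (1.8-month median, month 12). The late-entry share and delay distribution that would narrow this range are not in the Protocol.

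**What to change.** - **One cut-off.** Reconcile Figure 1 details, the inclusion criteria and Table A1 to a single data cut-off that leaves every entrant some follow-up. Define the screening period once, and align primary outcome 1 with the actual close of entry.
- **A per-participant clock.** Report completion of each step as cumulative incidence by a fixed time from the participant's own HPV report, for example six months. Censor anyone without the full window at the cut. With a month 12 cut, the last entrants then contribute about 3 months instead of being read as failures.
- **Times.** Estimate time outcomes, including primary outcome 3, with the same censoring, and label any summary among completers as such.

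The cost is wording, a small amount of extra analysis and possibly a later extract. The laboratory, NCSP and hospital records listed under Outcome measures and data management suffice. If all sites started on 19/8/22, recruitment closed on 19/2/23, entry on 19/5/23, and the last six-month window from testing on 19/11/23, before the January 2024 status statement; a later site start moves these dates. Whether approvals cover a later extract cannot be seen. Recruitment is complete, so the change affects analysis and reporting, not conduct. As analysis was already in progress, the report should say when the cut-off was chosen.

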# In some participants a cervical sample for HPV and cytology will be clinically recommended.

---

Objectives	Outcome measures

To describe the impact of HPV testing (by demographics and screening history when numbers permit) in terms of:
 
 
- Proportion of patients screened by each method
 
- Proportion of patients who complete or do not complete each step of the appropriate screening pathway (including uptake of screening, cytology triage, and colposcopy assessment) and referral back to primary care
 
- Screening outcomes in patients with prior abnormalities in relation to transition guideline recommendations
 
- Number of colposcopy referrals, their indication, and outcomes.
 
	
The number (and percentage) of participants that undertook a: vaginal test at home, vaginal test at their general practice without staff assistance, vaginal test at their general practice with staff assistance, cervical test without concurrent cytology, or cervical test with concurrent cytology.g
 
In participants who underwent HPV testing and had an unsatisfactory result, the number (and percentage) that: did have a repeat HPV test or did not have a repeat HPV test.
 
The reason cytology was performed in participants that had cytology results issued from the sample taken during a cervical HPV test. See figure legend for reasons.h
 
The reason cytology was performed in participants that had cytology performed after an HPV test and before colposcopy: positive for HPV result or other reason.*
 
The reason for no cytology report (prior to colposcopy) in participants positive for HPV and had a vaginal HPV test: cytology not considered feasible by the GP, participant declined, participant unable to be contacted, or other.*
 
The number (and percentage) of participants that had a referral for colposcopy by classification of urgency.*
 
In participants referred for colposcopy, the number (and percentage) that received 1, 2, 3 or >3 invitations for an appointment.*


To describe the impact of HPV testing (by demographics and screening history when numbers permit) in terms of time to completion of the appropriate screening pathway.
	
The distribution of times between an HPV test report being issued and GP referral for colposcopy.g, h
 
The mean and standard deviation or median and interquartile range for time from between various steps of the screening pathway, including invitation to screening, the study appointment, HPV testing and receipt of results, referral to follow up, and attendance at follow up. For specific detail on each of the outcome measures, see S Table 1.

To describe the disease burden detected in the study population, in terms of:
 
 
- HPV positivity rate by HPV 16/18 or other HPV, by demographics
 
- Incidence of CIN2+ in patients with HPV 16/18 by cytology result
 
- Incidence of CIN2+ in patients and with other HPV with abnormal cytology.
 
	
The number (and percentage) of participants who had the following HPV result: HPV 16, HPV 18, other HPV (listed by genotype where available), or HPV not detected.
 
In participants that had a cytology test prior to colposcopy, the number (and percentage) with each result. * See Figure legend for result options**
 
In participants that had a cytology test during colposcopy, the number (and percentage) with each result option. * See Figure legend for result options**
 
In participants that had colposcopy, results from the colposcopy, subsequent treatment recommendations and treatments. For further detail on each of these outcomes, see S Table 1.*
 
Incidence of CIN2+ in participants by cytology result.*


To describe uptake of screening by mode of invitation: Centralised or practice-based recall.
 
To describe resource utilisation (e.g. number of contacts, type of contact, engagement of other agencies, cost to patient) to achieve completion of the screening pathway: To achieve HPV screen, and in the event of an abnormal HPV screen, to achieve cervical cytology and/or colposcopy.
	
The number (and percentage) of participants with: 1,2,3 or >3 attempts to be contacted prior to their HPV test.
 
The number (and percentage) of participants who were successfully contacted to take part in the study by: letter, text, opportunistic invitation at their general practice, a face to face appointment with a staff member at their general practice, a phone call with a staff member from their general practice, other form of contact.
 
The mean and standard deviation of charges (NZD) for each type of HPV test listed under the outcome above. This will be reported by whether the tests were subsidised or not.
 
The number (and percentage) of participants informed of their HPV result by: * face to face appointment with a staff member at their GP clinic, phone call with a staff member from their general practice, text, other form of contact.
 
The number (and percentage) of participants with 0*, 1, 2 or 3 invitations for a cytology appointment, in participants who are recommended to have cytology.*
 
In participants that had a cytology test prior to colposcopy, the number (and percentage) informed of their cytology results by: * face to face appointment with a staff member at their general practice, phone call with a staff member from their general practice, text, other form of contact.
 
The mean and standard deviation for the per participant cost (NZD) to the participant's general practice for each of the following: HPV self-test at home or clinic without support, HPV self-test at clinic with support, HPV cervical test by a nurse, HPV cervical test by a doctor, cytology test as part of HPV cervical test, cytology test performed separately to the HPV test, and colposcopy referral.
 
Of note, deidentified data for non-participating patients will also be collected, including the number and nature of the attempts to invite them to have a cervical screening test during the recruitment period, and whether they opted to have a conventional cytology test.


To report the rate of unsatisfactory HPV samples or documentation.
	
In participants who underwent HPV testing and had an unsatisfactory result, the reason for that result: incorrect labelling, sample unsatisfactory, or other.

